##### 16.52 Secondary Outcome Analyses

- 16.522 Overall survival is defined as the time from registration to death due to any cause. The distribution of overall survival will be estimated using the method of Kaplan-Meier (Kaplan and Meier, 1958).

- 16.523 Progression-free survival is defined as the time from registration to the earliest date of documentation of disease progression or death due to any cause. The distribution of progression-free survival will be estimated using the method of Kaplan-Meier. We will also report the 1-year progression free survival (PFS) rate for the combination of anetumab ravtansine and atezolizumab in 2nd-line NSCLC.
- 16.524 Adverse Events: All eligible patients that have initiated treatment will be considered evaluable for assessing adverse event rate(s). The maximum grade for each type of adverse event will be recorded for each patient, and frequency tables will be reviewed to determine patterns. Additionally, the relationship of the adverse event(s) to the study treatment will be taken into consideration.
- 16.53 Correlative Analyses: Due to the small overall sample size, the results of these analyses will be considered exploratory and hypothesis-generating in nature.
- To determine using flow cytometry the levels of Bcl-2 interacting mediator of cell death (BIM) in circulating CD8+ CD11a+ PD-1+ T-cells, in peripheral blood samples collected from patients prior to initiation of therapy (baseline) and correlating these with ORR during and following treatment with the combination regimen. We'll also determine tissue MSLN and PD-L1 expression and correlate with response to combination therapy with atezolizumab and anetumab ravtansine. Finally, we'll correlate baseline serum soluble PDL-1 (sPDL-1) with response to therapy. These data will be explored in a descriptive manner using basic data summaries and graphics.
- 16.54 Over Accrual: If more than the target number of patients are accrued, the additional patients will not be used to evaluate the final decision rule or used in any decision making processes; however, they will be included in final endpoint estimates and confidence intervals.
- 16.6 Data & Safety Monitoring:
- 16.61 The principal investigator(s) and the study statistician will review the study at least twice a year to identify accrual, adverse event, and any endpoint problems that might be developing. The Mayo Clinic Cancer Center (MCCC) Data Safety Monitoring Board (DSMB) is responsible for reviewing accrual and safety data for this trial at least twice a year, based on reports provided by the MCCC Statistical Office.
- 16.62 Adverse Event Stopping Rules: The stopping rules specified below are based on the knowledge available at study development. We note that the Adverse Event Stopping Rule may be adjusted in the event of either (1) the study re-opening to accrual or (2) at any time during the conduct of the trial and in consideration of newly acquired information regarding the adverse event profile of the treatment(s) under investigation. The study team may choose to suspend accrual because of unexpected adverse event profiles that have not crossed the specified rule below.
- 16.621 Phase I (includes all phase I patients):  
By the nature of the "cohorts of three" phase I study design, stopping rules are in place for each dose level. Specifically, if 2 or more dose-limiting toxicities (DLTs) are observed during cycle 1 at any given dose level, accrual to that dose level will be stopped, and patients will

be accrued to the next lower dose level until a maximum of 6 patients are treated at the lower level. Note that a DLT that affects dose escalation is only that which is observed in the first cycle of treatment.

16.622 Phase II (includes all phase II patients, including phase I patients treated at the MTD):

Accrual will be temporarily suspended to this study if at any time we observe events with an attribution of possibly, probably, or definitely related to study treatment that satisfy one of the following:

- If 5 or more patients in the first 15 treated patients experience a grade 4 or higher non-hematologic adverse event
- If after the first 15 patients have been treated, 33% of all patients experience a grade 4 or higher non-hematologic adverse event.

We note that we will review grade 4 and 5 adverse events deemed “unrelated” or “unlikely to be related”, to verify their attribution and to monitor the emergence of a previously unrecognized treatment-related adverse event.

16.7 Results Reporting on ClinicalTrials.gov:

At study activation, this study will have been registered within the “ClinicalTrials.gov” website. The Primary and Secondary Endpoints along with other required information for this study will be reported on [www.ClinicalTrials.gov](http://www.ClinicalTrials.gov). For purposes of timing of the Results Reporting, the initial estimated completion date for the Primary Endpoint of this study is 3 years after the study opens to accrual. The definition of “Primary Endpoint Completion Date” (PECD) for this study is at the time the last patient registered has been followed for at least 6 months.

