#### Phase II

2.23 To determine the progression-free survival (PFS) and the 1-year PFS rate for the combination of anetumab ravtansine and atezolizumab in 2nd-line NSCLC

2.24 To determine the overall survival of anetumab ravtansine combined with atezolizumab in second-line therapy of NSCLC

2.25 Adverse events will also be summarized as well.

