#### 13.7 Ineligible

A patient is deemed *ineligible* if after registration, it is determined that at the time of registration, the patient did not satisfy each and every eligibility criteria for study entry. The patient may continue treatment off-protocol at the discretion of the physician as long as there are no safety concerns, and the patient was properly registered. The patient will go directly to the event-monitoring phase of the study (or off study, if applicable).

- If the patient received treatment, all data up until the point of confirmation of ineligibility must be submitted. Event monitoring will be required per Section 4.0 of the protocol.
- If the patient never received treatment, on-study material must be submitted. Event monitoring will be required per Section 4.0 of the protocol.

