- 16.28 Dose de-escalation: If DLT meets the stopping boundaries set by the above dose escalation algorithm at dose level 1 (for example, more than 1 out of 3 patients or more than 1 out of 6 patients), the next cohort of three patients will be entered at a dose level of -1. Further dose re-escalation will depend on the toxicity profile observed at dose level -1, and re-evaluation of the regimen by the study team may be done.
- 16.29a If a patient fails to complete the initial course of therapy (defined as drug administration and 21 days) for reasons other than DLT defined adverse events, the patient will be regarded as uninformative in regard to the primary study goal and an additional patient will be treated at the current dose level; however, all toxicity information will be utilized in the analysis.
- 16.29b Operating Characteristics for Phase I portion of trial

The following table gives the probability of dose escalation at a single dose level as a function of the true probability of DLT at that level using the Cohort 3+3 design described in section 16.2.

| True Rate of DLT (%) | Probability of Dose Escalation |
|----------------------|--------------------------------|
| 10                   | 0.91                           |
| 20                   | 0.71                           |

|    |      |
|----|------|
| 30 | 0.49 |
| 40 | 0.31 |
| 50 | 0.17 |

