#### 16.31 Adverse Events Profile

The number and severity of all adverse events (overall and by dose-level) will be tabulated and summarized in this patient population. The Grade 3+ adverse events will also be described and summarized in a similar fashion. This will provide an indication of the level of tolerance for this treatment combination in this patient group.

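### Phase II adverse-event rates count only eligible treated patients, so patients dosed and later ruled ineligible drop out of the reported rates

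*Combined protocol and SAP*

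**What the plan says.** The phase II safety goal in section 2.25 names no population: "Adverse events will also be summarized as well". The population is set in 16.524, within the phase II analysis plan: "All eligible patients that have initiated treatment will be considered evaluable for assessing adverse event rate(s").

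Under 13.7, a patient is ineligible if it is found after registration that, at registration, "the patient did not satisfy each and every eligibility criteria for study entry". One missed criterion is enough. The section expects that some such patients will already have been dosed: "If the patient received treatment, all data up until the point of confirmation of ineligibility must be submitted". They then move to event monitoring, and any further treatment is off protocol.

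Three other safety provisions carry no eligibility condition:

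- **16.622, phase II stopping rule.** Its scope is "Phase II (includes all phase II patients, including phase I patients treated at the MTD"), and its first limb reads "If 5 or more patients in the first 15 treated patients experience a grade 4 or higher non-hematologic adverse event".
- **16.31, phase I tabulation.** "The number and severity of all adverse events (overall and by dose-level) will be tabulated and summarized in this patient population".
- **16.29a, phase I patients replaced as uninformative.** For them, "all toxicity information will be utilized in the analysis".

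**The concern.** Adverse-event rates describe what happened to people who were exposed. A patient dosed and then ruled ineligible was exposed in the same way as any other. There is a case for limiting a response analysis to eligible patients, because the target population defines that question. The case does not carry over to toxicity.

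Two things are at stake. First, the monitored and reported populations differ within section 16: an event in a treated ineligible patient can help trigger the 16.622 suspension and then be missing from the phase II rates. A phase I patient treated at the MTD who is later ruled ineligible would appear in the phase I tables but not in the phase II rates, although 16.41 and 16.622 count MTD patients in phase II.

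Second, adverse events are a phase II secondary goal, and 16.7 says that secondary endpoints will be reported on the public registry. The restricted rates would therefore be the published phase II safety result. Some eligibility criteria plausibly relate to toxicity risk, such as marrow, renal and hepatic function (section 3.2), corneal disease (3.39m) and recent steroid use (3.39f). A patient who missed one of these might be more likely than average to have an event.

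**Working it through.** The plan states no figure for this point, so there is none to reproduce. The check is a reading of the provisions, followed by simple proportions under stated assumptions.

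**Step 1. Is the restriction deliberate, and is it undone elsewhere?**

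| Provision | Use | Limited to eligible patients? |
|---|---|---|
| 16.33 | Phase I response | Yes, stated |
| 16.511 | Phase II response | Yes, stated; major violations also excluded |
| 16.524 | Phase II adverse-event rates | Yes, stated |
| 16.31, 16.29a | Phase I adverse events and toxicity | No |
| 16.622 | Phase II stopping rule | No |
| 10.41 | Serious adverse event reporting | No |

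Where the plan wants an eligibility limit it writes one. No section puts treated ineligible patients back into the 16.524 rates, and no all-treated safety population is defined.

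**Step 2. Share of treated patients left out.**

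Inputs: 37 eligible patients in the final phase II analysis (16.42), and k treated patients later found ineligible. The documents give no value for k, so k = 1 to 6 is an assumption. The upper end borrows the size of the replacement allowance in 16.12 only as a convenient limit; it is not a forecast.

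Share omitted = k / (37 + k)

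- k = 1: 1/38 = 2.6%
- k = 3: 3/40 = 7.5%
- k = 6: 6/43 = 14.0%

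The 43 here is 37 + 6 treated phase II patients. It is not the 43 in 16.12, which adds phase I patients from another dose level.

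**Step 3. Effect on a reported rate.**

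Let p_E be the event rate in eligible patients and p_I the rate in treated ineligible patients. Then:

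all-treated rate − reported rate = [k / (37 + k)] × (p_I − p_E)

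The reported rate is too low if p_I exceeds p_E and too high if it is smaller. For illustration, assume 4 of 37 eligible patients have a given event, so the plan reports 4/37 = 10.8%.

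| k | No omitted patient has the event | All omitted patients have it |
|---|---|---|
| 1 | 4/38 = 10.5% | 5/38 = 13.2% |
| 3 | 4/40 = 10.0% | 7/40 = 17.5% |
| 6 | 4/43 = 9.3% | 10/43 = 23.3% |

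With k = 0 the two rates are identical.

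**Step 4. Does the fix disturb the design?**

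No. The two-stage rule (stop at 3 or fewer responses in 17; promising at 11 or more in 37) uses response counts in eligible patients. Its exact type I error is 0.0948 at a 20% response rate and its power is 0.903 at 40%, in line with the stated limits. Neither depends on the adverse-event denominator.

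**The case against.** The strongest reply is that little depends on the 16.524 denominator. It feeds a descriptive summary with no test or threshold. Safety decisions run on the 16.622 rule, on expedited reporting and on DSMB review at least twice a year (16.61), none of which excludes ineligible patients. Eligibility is also verified at registration (6.232), which should keep the number affected small. All of this stands, and it limits the point to the phase II reported rates.

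It can also be said that the mismatch with 16.622 rests on that section's silence about eligibility. That is true, but the plan states the limit elsewhere when it wants one, so counting all treated patients is the natural reading.

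Four stronger readings are tempting and are not supported:

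- **That the trial's safety results as a whole omit these patients.** Sections 16.31 and 16.29a cover phase I without an eligibility limit.
- **That the 6 extra patients in 16.12 (49 against 43) measure the number omitted.** Those totals mix the two phases, and the 6 are for patients needing replacement. The explicit replacement rules (13.6 and 16.29a) concern phase I patients who do not complete cycle 1. Phase II ineligible patients might also be replaced, since 16.41 and 16.42 count eligible patients, but nothing assigns all 6 to that group.
- **That the rates must be understated.** Many criteria, such as mesothelin score, measurable disease or age of archival tissue, have no evident link to toxicity.
- **That this is the first human use of the combination.** Section 1.4 gives a mechanistic and preclinical rationale, but the documents do not say that the pair has never been given together.

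**Conclusion.** The point holds for the phase II adverse-event rates. Section 16.524 is an explicit rule that removes exposed patients from a secondary safety result, and it is out of line with the plan's other safety provisions.

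Its size cannot be fixed from the documents because no ineligibility rate is given. The range of 2.6% to 14.0% of treated patients omitted rests entirely on assuming 1 to 6 such patients beside 37 eligible ones. The direction of bias is open: understatement is plausible when the missed criterion bears on toxicity risk, but it is not established. The primary endpoint and safety monitoring during the trial are not threatened. The change is worth making because the omission serves no purpose in a safety summary and is cheap to remove.

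**What to change.** Make two linked changes.

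1. **Section 16.524.** Replace the evaluability sentence with: *All patients who receive any dose of either study drug, regardless of eligibility, are included in the adverse-event analysis.* This matches the population that 16.622 already counts.
2. **Section 13.7.** State that adverse-event data from treated ineligible patients are collected over the same safety window as for other patients. At present submission is required only until ineligibility is confirmed. Without this second change, these patients would enter a maximum-grade-per-patient table with shortened follow-up, which could itself lower the rates.

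The cost is about two sentences of text and some added adverse-event data collection for the patients concerned. Sample size, type I error and power stay as they are.

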16.8 Inclusion of Women and Minorities

This study will be available to all eligible patients regardless of race, gender, or ethnic group. There is no information currently available regarding differential agent effects of either regimen in subsets defined by gender, race, or ethnicity, and there is no reason to expect such differences exist. Therefore, although the planned analyses will, as always, look for differences in treatment effect based on gender and racial groupings, the sample sizes are not increased in order to provide additional power for such subset analyses.

To predict the characteristics of patients likely to enroll in this trial we have reviewed the Mayo registration classified by race and gender. This revealed that roughly 3% of patients registered into cancer trials during the past three years could be classified as minorities and about 60% of patients were women. This would suggest that only 2 patients in the study sample are expected to be classified as minorities. This precludes the possibility of a separate subset analysis beyond simple inspection of results for the minority patients. Expected sizes of racial by gender subsets are shown in the following table:

| Accrual Targets                        |                   |              |              |
|---|-------------------|--------------|--------------|
| Ethnic Category                        | Sex/Gender |              |              |
|   | Females    | Males | Total |
| Hispanic or Latino                            | 1                 | 1            | 2            |
| Not Hispanic or Latino                        | 28                | 19           | 47           |
| Ethnic Category: Total of all subjects | 29         | 20    | 49    |

| Racial Category                        |           |           |           |
|---|-----------|-----------|-----------|
| American Indian or Alaskan Native             | 0         | 0         | 0  |
| Asian   | 0         | 1         | 1  |
| Black or African American                     | 1         | 0         | 1  |
| Native Hawaiian or other Pacific Islander     | 0         | 0         | 0  |
| White   | 28        | 19        | 47 |
| Racial Category: Total of all subjects | 29 | 20 | 49 |

|                           |   |
|---------------------------|---|
| Ethnic Categories: | 
Hispanic or Latino – a person of Cuban, Mexican, Puerto Rican, South or Central American, or other Spanish culture or origin, regardless of race. The term “Spanish origin” can also be used in addition to “Hispanic or Latino.”
 
Not Hispanic or Latino
  |
| Racial Categories: | 
American Indian or Alaskan Native – a person having origins in any of the original peoples of North, Central, or South America, and who maintains tribal affiliations or community attachment.
 
Asian – a person having origins in any of the original peoples of the Far East, Southeast Asia, or the Indian subcontinent including, for example, Cambodia, China, India, Japan, Korea, Malaysia, Pakistan, the Philippine Islands, Thailand, and Vietnam. (Note: Individuals from the Philippine Islands have been recorded as Pacific Islanders in previous data collection strategies.)
 
Black or African American – a person having origins in any of the black racial groups of Africa. Terms such as “Haitian” or “Negro” can be used in addition to “Black or African American.”
 
Native Hawaiian or other Pacific Islander – a person having origins in any of the original peoples of Hawaii, Guam, Samoa, or other Pacific Islands.
 
White – a person having origins in any of the original peoples of Europe, the Middle East, or North Africa.
 |

## 17.0 Tissue Biospecimens/Pathology Considerations

### 17.1 Summary Table of Research Tissue Specimens to be collected

| Correlative Study (Section for more information) | Mandatory or Optional                    | Type of Tissue to Collect | Blocks/Slides /Cores                             | Collection       | Process at site | Storage /Shipping |
|--|--|---------------------------|--|------------------|-----------------|-------------------|
| Archived   | Mandatory                                | Paraffin embedded         | 1 H&E slide and 2 unstained 4 micron plus slides | Pre-registration | Yes             | Ambient           |
| Fresh tissue biopsy                              | Mandatory only if archival not available | Fresh                     | 1-2 cores  | Pre-registration | Yes             | Ambient           |

### 17.2 Tissue collection and processing

Mandatory tissue collection at baseline for IHC mesothelin testing. If archival tissue is not available, a fresh biopsy must be completed. Criteria for the submission of tissue are:

- Archival tissue must have been collected within 36 months prior to registration, not previously irradiated, and after diagnosis of metastatic disease.

#### 17.21 Biopsy Procedure

If archival tissue not available a tumor biopsy will be obtained at baseline. If a site is deemed appropriate for biopsy with minimal risk to the participant by agreement between the investigators an attempt for biopsy will be made. Because approximately 20% of tumor biopsies collected on research trials are not usable due to the presence of stroma or normal and/or necrotic tissue and paired biopsies are necessary for analysis, up to 5 core biopsies 18-gauge in diameter and  $\geq 1$  cm in length will be obtained during each procedure to try and ensure adequate tumor content and quality. Cores from different areas of the tumor are preferred when feasible. An H&E stain for each core to identify whether the core actually contains tumor or not. Unstained slides for staining will need to be prepared from the cores. Acceptable biopsy procedures are:

- Percutaneous biopsy with local anesthetic.
- Excisional cutaneous biopsy with local anesthetic
- Other biopsy with local anesthetic and/or sedation that has been shown to have a risk of severe complications  $< 2\%$

17.22 Tissue kits will not be provided for this protocol.

#### 17.23 Tissue submission

17.231 Submit 1 H&E slide and 2 unstained 4 micron plus slides for archival tissue and 1-2 tissue cores at baseline and if applicable, at disease progression.

17.232 The samples should be sent directly to the IHC Lab. If lab is not local, send by FedEx standard next day delivery service. Ship only Monday to Thursday to avoid delivery on a weekend. Ship samples to:

Mayo Clinic

Telephone:

### 17.3 Mesothelin tissue analysis

Preclinical and Phase I evidence suggests that mesothelin expression (or expression level above a certain threshold) in human tumors may be required for binding, internalization, and anti-tumor activity of anetumab ravtansine. Mesothelin expression will be prospectively evaluated for patient selection. All patients will provide formalin-fixed, paraffin-embedded (FFPE) tumor samples or fresh tissue to analyze mesothelin expression as a potential predictive biomarker. If archival material is not available a fresh biopsy can be taken, if the investigator deems the procedure to be safe for the patient. Patients will be stratified to the appropriate cohort based on the following criteria: High mesothelin expression of  $\geq 30\%$  of viable tumor cells with 2+ or 3+ membrane staining intensity will be in the “mesothelin high” group. Low-mid mesothelin expression of at least 5% viable tumor cells positive for MSLN expression (all intensities) but  $< 30\%$  2+ or 3+ membrane staining will be in the “mesothelin low” group. The IHC test used to detect mesothelin expression (Ventana MSLN [SP74] IHC assay) is currently investigational and not approved by FDA or other regulatory authorities. Both groups will be enrolled in the phase I dose escalation portion but only the “mesothelin high” group will be enrolled in the phase II expansion portion of the study.

